**Figure 2: Trial flow chart**

Abbreviations: N: number of participants in corresponding treatment arm; PQP: Piperaquine; PYR: Pyronaridine.

As long as the data from the sentinel group demonstrate acceptable safety and tolerability, the participants in the non-sentinel group will be discharged on Day 5, but this decision will be made by the Safety Review Committee (SRC) (See Table 7). The Day 6 OP visit will apply to the non-sentinel group only.

**Table 5: Schedule of Assessments**

Procedure	Screening (D-22 to D-2)	D-1	D1	D2	D3	D4	D5	D6	D7  Sentinel Group only	D8	D15	D22	Last visit D30 (±1)	
In-house stay		X	X	X	X	X	X 	X	X					
Outpatient visit								X		X	X	X	X	
Informed consent	X													
Eligibility check	X	X												
Medical history/ demographics	X	X 												
Prior & concomitant medications	X	X	X	X	X	X	X	X	X	X	X	X	X	
Smoking history and current	X													
Beck depression inventory questionnaire	X													
Urine drugs of abuse screen	X	X												
Alcohol breath test	X	X												
Serology HIV 1&2, Hepatitis B&C	X													
Serum pregnancy test (females)	X	X											X	
FSH (post- menopausal females)	X													
Randomisation			X											
Trial drug administration 			X	X	X									
Meals 		X	X	X	X	X	X	X	X	X				
Safety and tolerability:														
Vital signs 	X	X	X	X	X	X	X	X	X	X	X	X	X	
12-lead ECG 	X	X	X	X	X	X	X	X	X	X	X	X	X	
24-hour Holter ECG	X													
Telemetry 			X	X	X									
BMI calculation	X	X 												
Physical examination 	X	X	X	X	X	X	X	X	X	X			X	

Procedure	Screening (D-22 to D-2)	D-1	D1	D2	D3	D4	D5	D6	D7  Sentinel Group only	D8	D15	D22	Last visit D30 (±1)	
Biochemistry, Haematology, Coagulation 	X	X	X	X 	X 	X	X	X	X	X	X	X	X	
Urinalysis	X	X	X		X		X		X	X	X	X	X	
Pharmacokinetics:														
PK sampling – PYR 			X	X	X	X		X		X	X	X		
PK sampling – PQP  (including e.g. N- oxidated metabolite)			X	X	X	X		X		X	X	X		
Pharmacogenomics:														
CYP polymorphism				X										

1. Vital signs (supine blood pressure, heart rate and respiratory rate) will be measured after rest of at least five minutes in supine position. Tympanic body temperature will be taken at each time-point (resting in supine position is not required for body temperature). Standing blood pressure and heart rate will be performed one minute after standing to assess for orthostatic change at screening and on Day -1, Day 1 and Day 3. See Table 6 for Time-points.
2. 12-lead ECG will be measured in triplicate after a rest period of at least ten minutes in supine position. See Table 6 for time-points.
3. Full physical examination at screening and last visit only. Symptom-directed physical examinations at other time-points.
4. See Table 13 for details of laboratory parameters to be measured.
5. Plasma samples for PQP and blood samples for PYR. See Table 6 for time-points.
6. Continuous 12-lead telemetry will be recorded from at least one hour pre-dose on Day 1 to 24 hours post-dose on Day 3.
7. Update only on Medical History at admission.
8. On Day -1, only weight will be collected and height from screening will be used for BMI calculation.
9. Standard meals will be served at standard unit times. On Days 1, 2 and 3 the first meal will be lunch given four hours post-dose. Meals will be optional on the discharge day.
10. Dosing will be carried out in fasted state on the morning of each dosing day (Days 1, 2 and 3), firstly with PYR/ placebo tablets, followed by PQP/ placebo tablets.
11. Participants in the sentinel group will remain in-house until Day 7. If there are no clinically concerning safety signals, the remaining participants subsequently dosed (from the main group) will remain in-house until Day 5.
12. On Day 2 and Day 3, only the following safety blood tests will be measured: AST, ALT, bilirubin.

Note: COVID-19 tests will be carried out at regular intervals, prior to entry in the unit and throughout the residential period as per the latest RPL COVID-19 Infection Control Guidelines and pre-entry algorithms.

Abbreviations: AE: Adverse Event; BMI: body mass index; D: Day (where Day 1 is the first day that IMPs are administered); ECG: electrocardiogram; FSH: Follicular Stimulating Hormone; PK: pharmacokinetic; PQP: piperaquine; PYR: pyronaridine.

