## **2.2 Endpoints**

### **2.2.1 Primary**

- The incidence, severity and relationship of Treatment-Emergent Adverse Events (TEAEs).
- Proportion of participants with clinically significant changes in laboratory safety tests (haematology, biochemistry, coagulation and urinalysis).
- Proportion of participants with morphological and/or rhythm abnormalities on electrocardiogram (ECG).
- Proportion of participants with clinically significant changes in ECG time intervals (PR, QRS, QT and QTc intervals) and clinically significant changes against baseline Holter.
- Proportion of participants with clinically significant changes in vital signs (systolic blood pressure, diastolic blood pressure and pulse rate).

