**Table 6 Schedule of Assessments (continued)**

Trial Day	Time (h)	PK sampling 	12-lead ECG 	Vitals 	Meals 
D1	-1.5		X		
	-1		X		
	-30 mins	X	X	X	
	1	X	X	X	
	2	X	X	X	
	3	X	X		
	4	X	X		X
	5	X	X	X	
	6	X	X		
	7	X	X		
	8	X	X	X	
	10				X
	12	X	X		X
D2	-1.5		X		
	-1		X		
	-30 mins	X	X	X	
	4	X	X	X	X
	6	X	X	X	
	10				X
	12	X	X	X	X
D3	-1.5		X		
	-1		X		
	-30 mins	X	X	X	
	-5 mins		X		
	1	X	X	X	
	2	X	X	X	
	3	X	X		
	4	X	X		X
	5	X	X	X	
	6	X	X		
	7	X	X		
	8	X	X	X	
	10				X
	12	X	X		X

1. Plasma samples for PQP and blood samples for PYR.
2. 12-lead ECG will be measured in triplicate after a rest period of at least ten minutes in supine position.
3. Vital signs will be measured after rest of at least five minutes in supine position. Standing vitals will be performed after one minute in the upright standing position, to assess for orthostatic change, on Screening, Day -1, and on Day 1 and Day 3 at pre-dose (-30 min) and post dose at 5h.
4. On dosing days, participants will fast from all food and drink (excluding water) at least three hours pre-dose and four hours post-dose. Participants may drink water until one hour before dosing and may re-commence water one hour subsequent to dosing.
5. Four-hour procedures to be completed prior to lunch being given

Abbreviations: D: day; ECG: electrocardiogram; h: hours (where hour 0 is the time at which the first IMP is administered); mins: minutes; PK: pharmacokinetic.

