### 2.2 Endpoints

#### Primary

- The incidence, severity and relationship of Treatment-Emergent Adverse Events (TEAEs).
- Proportion of participants with clinically significant changes in laboratory safety tests (haematology, biochemistry, coagulation and urinalysis).

- Proportion of participants with morphological and/or rhythm abnormalities on electrocardiogram (ECG).
- Proportion of participants with clinically significant changes in ECG time intervals (PR, QRS, QT and QTc intervals) and clinically significant changes against baseline Holter.
- Proportion of participants with clinically significant changes in vital signs (systolic blood pressure, diastolic blood pressure and pulse rate).

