## **4. STATISTICAL ANALYSES**

### **4.1 General Notes for Statistical Analyses**

In general, descriptive statistics for continuous variables will include number of non-missing values (n), arithmetic mean, standard deviation (SD), median, minimum, and maximum.

Descriptive statistics for PK parameters will include N - the number of participants, n - the number of samples, n(LLOQ) - the number of samples <LLOQ (lower limit of quantification), arithmetic mean, SD - standard deviation, CV - coefficient of variation, geometric mean, median, minimum, maximum.

Categorical variables will be summarized using frequency counts and percentages.

For all tables, except PK parameter tables, descriptive statistics for minimum and maximum will be presented with the same decimal digits as the original data, and with 1 more decimal place than the original data for mean and median; SD and SE will be reported with 2 more decimal places than the original data. Degrees of freedom based on the Kenward Roger approximation will be presented with one decimal.

PK parameters will be presented as follows in the listing:  $C_{\max}$  and  $t_{\max}$  will be presented as given in the raw data; other PK parameters will be presented with 3 decimal places. Descriptive statistics for PK parameters will be presented with decimal places as appropriate for the particular parameter and treatment group.

The analyses will be presented by treatment group (2 monotherapies, combination therapy and placebo), overall as well as stratified by body weight group:

- < 65 kg
- 65 - < 75 kg
- $\geq$  75 kg.

- Treatment arm 1:
  - PYR 540 mg + PQP 960 mg
  - PYR 720 mg + PQP 960 mg
  - PYR 720 mg + PQP 1280 mg
- Treatment arm 2
  - PYR 540 mg
  - PYR 720 mg
- Treatment arm 3
  - PQP 960 mg
  - PQP 1280 mg
- Overall (for safety set)
- Placebo

All collected data will be presented in by-subject listings. Listings will be ordered by treatment group, body-weight group and subject number and will include all randomized subjects.

Unless otherwise stated, baseline will be defined as the last non-missing value prior to first administration of study drug. Changes from baseline values will be calculated as the post-baseline assessment value minus the baseline value. Only observed values from scheduled time points will be used to create summary tables.

Deviations from the planned analyses will be described in the final clinical study report (CSR).

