## 4.11.3 Vital Signs

Vital signs data (SBP, DBP, Pulse rate, temperature) will be listed for individual subjects. Summary statistics of absolute (observed) values and changes from baseline will be calculated for each parameter and scheduled timepoint by treatment group.

Out-of-reference-range values will be flagged as high (H) or low (L) and as being clinically relevant or not: the number of subjects presenting out-of-range and clinically relevant values will be summarised.

Parameter	Normal Range
Temperature (tympanic)	35-37.5°C
Systolic Blood Pressure (Supine)	90-140 mmHg
Diastolic Blood Pressure (Supine)	40-90 mmHg
Postural Drop (systolic, symptomatic)	≤20 mmHg drop
Pulse Rate (supine)	40-100 bpm
Respiratory Rate	8-20 breaths per min

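### Standing blood pressure and heart rate are taken to assess orthostatic change, but the SAP counts only symptomatic systolic drops and specifies no standing-minus-supine variable

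*Protocol*

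**What the plan says.** **Collection.** Footnote 1 to Protocol Table 5 gives the purpose of the standing readings: "Standing blood pressure and heart rate will be performed one minute after standing to assess for orthostatic change". They are taken at screening and on Day -1, and footnote 3 to Table 6 adds the dosing-day times: "on Day 1 and Day 3 at pre-dose (-30 min) and post dose at 5h". Supine vital signs are scheduled at the same times, so each standing value has a supine partner and each 5 h pair has a same-day pre-dose pair.

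**Endpoint.** One primary endpoint, in both documents, is the proportion of participants with "clinically significant changes in vital signs (systolic blood pressure, diastolic blood pressure and pulse rate". The primary objective asks for comparison with placebo.

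**Analysis.** SAP 4.11.3 opens with the variables: "Vital signs data (SBP, DBP, Pulse rate, temperature) will be listed for individual subjects". Position is not stated. It continues: "Summary statistics of absolute (observed) values and changes from baseline will be calculated for each parameter and scheduled timepoint by treatment group". SAP 4.1 defines change in one way only: "Changes from baseline values will be calculated as the post-baseline assessment value minus the baseline value". The range table in 4.11.3 labels systolic pressure, diastolic pressure and pulse as supine. Its single postural row is "Postural Drop (systolic, symptomatic", with a drop of 20 mmHg or less as normal. Participants with out-of-range and clinically relevant values are counted. Protocol 10.3 adds no postural analysis.

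**The concern.** The measurement has a declared purpose, and the analysis section does not carry that purpose through. As the postural row is worded, a fall in systolic pressure of any size is within range if the participant reports nothing. A diastolic fall or a postural rise in heart rate has no criterion at all.

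Three features of the trial make this worth correcting.

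- **Timing.** The 5 h reading falls at about the stated piperaquine tmax and inside the stated 2 to 8 h window for the pyronaridine peak (Protocol 1).
- **Overlapping effects.** Protocol 1 names dizziness among the overlapping effects of the two drugs, and this is their first combined use in humans.
- **Blinding.** The bitter taste of piperaquine cannot be masked. Protocol 6.2.2 and SAP 3.3 accept this because the key safety endpoints are objective. Making a blood-pressure criterion depend on symptoms adds a subjective element to an otherwise objective reading.

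What is at stake is a by-arm count and summary of postural change on a primary safety domain, using data the trial already collects.

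**Working it through.** **1. Match what is measured to what is specified.**

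| Postural finding | Criterion in SAP 4.11.3 | Counted by arm? |
|---|---|---|
| Systolic drop >20 mmHg, symptomatic | Yes | Yes |
| Systolic drop >20 mmHg, asymptomatic | No | No |
| Diastolic drop | No | No |
| Postural heart-rate change | No | No |
| Standing minus supine as a continuous variable | Not specified | Not explicitly |

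Change from baseline compares two times in one position. Postural change compares two positions at one time. The SAP's definition of change does not produce the second.

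**2. Could the planned summaries supply it indirectly?** If standing and supine values were tabulated separately in the same participants, the mean postural change would follow as mean standing minus mean supine. Its standard deviation would not, because that needs the within-person covariance. Nor would the number of participants who dropped. If both readings were held under one parameter, SAP 4.1 uses the first scheduled value at a time point, and Protocol 3.2 lists supine before standing. The standing value could then fall out of the summary. The SAP does not say which arrangement applies.

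**3. The plan's own detection figure.** Protocol 10.7 and SAP 3.2 give the chance of at least one event in 16 combination participants, which is 1 - (1 - p)^16.
- p = 0.10: 1 - 0.90^16 = 0.815 (stated 81%).
- p = 0.20: 1 - 0.80^16 = 0.972 (stated 97%).

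Both reproduce. If the event is a systolic drop above 20 mmHg and a share f of such drops is symptomatic, the SAP rule detects at rate p × f, so the chance is 1 - (1 - pf)^16. The documents do not give f, so it is an assumption shown over a range.

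| True rate p | f = 1 | f = 0.5 | f = 0.25 |
|---|---|---|---|
| 10% | 81% | 56% | 33% |
| 20% | 97% | 81% | 56% |

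**4. Illustrative numbers of participants.** These inputs are assumptions, not document figures: normally distributed supine-to-standing systolic drop, SD 8, 10 or 12 mmHg, mean drop 3 mmHg on placebo, and the drugs adding d mmHg.

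P(drop > 20) = 1 - Φ((20 - 3 - d)/SD)

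- d = 0: 17/8, 17/10, 17/12 give 0.017, 0.045, 0.078; × 16 = 0.3, 0.7, 1.3.
- d = 5: 12/8, 12/10, 12/12 give 0.067, 0.115, 0.159; × 16 = 1.1, 1.8, 2.5.
- d = 10: 7/8, 7/10, 7/12 give 0.191, 0.242, 0.280; × 16 = 3.1, 3.9, 4.5.

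With f from 0.25 to 0.5, the SAP rule would count about 0.3 (1.07 × 0.25) to 1.3 (2.54 × 0.5) of 16 at d = 5. At d = 10 it would count about 0.8 (3.05 × 0.25) to 2.2 (4.48 × 0.5). The d = 0 row shows that some drops are expected without any drug effect, so the count needs the placebo arm beside it.

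The arm size of 16 is the planned one. SAP 3.2 records that recruitment stopped at 37 and does not give the split by arm.

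**The case against.** The strongest case against is that this is an ambiguity of wording with little behind it.

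- **Postural drop is already a parameter.** It sits under the parameter heading of the range table, and summaries are promised for each parameter. This stands in part: a reader could compute and tabulate the systolic drop on that basis. But the row is restricted to symptomatic drops. The same table also carries respiratory rate, which is absent from the list of analysed variables, so it cannot be taken as that list.
- **The data are not lost.** SAP 4.1 lists all collected data by subject, symptomatic systolic drops are counted, and standing values may enter the summaries because position is unstated. This stands. A reader might infer that the standing data are never summarised or go unused, and the documents do not support that. Listings, however, give no proportion by arm.
- **Adverse event reporting would catch it.** Dizziness would appear in the TEAE tables, and an investigator may judge any value clinically relevant or an AE. That is fair for symptomatic cases. For an asymptomatic drop needing no further testing or intervention, Protocol 8.1 leaves AE status to judgement. Protocol 8.3 discourages recording as AEs signs captured by other protocol methods, with limited exceptions.
- **The 5 h reading follows lunch at 4 h.** All arms eat on the same schedule, so the meal is balanced in any by-arm table. This stands. It supports showing placebo alongside and is not a separate flaw.
- **Little prior expectation.** Orthostatic hypotension is not among the three toxicities of focus, and the risk tables do not list it. SAP 4.11 disclaims formal statistical analysis of safety. This stands and limits the weight of the point.

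**Conclusion.** The point holds as a gap between the stated purpose of a measurement and its planned output. Under SAP 4.11.3 as written, asymptomatic systolic drops above 20 mmHg, diastolic drops and postural heart-rate changes would not be counted or explicitly summarised by arm. It is a worthwhile, inexpensive improvement and does not threaten the trial's validity.

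The size is illustrative only. With an SD of 8 to 12 mmHg and a 3 mmHg placebo drop, about 1 to 2.5 of 16 would exceed the SAP's limit if the drugs add 5 mmHg, and about 3 to 4.5 of 16 if they add 10 mmHg, with only the symptomatic share counted. The result turns on the assumed drug effect, for which the documents give no figure.

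Two stronger readings should be resisted. A reader might infer that symptoms are not recorded with the standing reading because Tables 5 and 6 show no such entry. Those tables schedule procedures, and the CRF is not among the documents, so this cannot be judged. A reader might also infer that the trial is missing a test it could have won. The safety analysis is descriptive, and no claim about statistical significance follows from this point.

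**What to change.** In SAP 4.11.3:

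1. State the position (supine or standing) used in each vital-signs table.
2. Derive standing minus supine systolic pressure, diastolic pressure and pulse at each paired time.
3. Summarise these differences, and their change from Day 1 pre-dose, descriptively by treatment group including placebo at 5 h on Days 1 and 3.
4. Count participants with a systolic drop above the SAP's existing 20 mmHg limit regardless of symptoms, and keep symptomatic cases as a sub-row so the current count is preserved.

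Whether to set a limit for diastolic or heart-rate change is for the sponsor; descriptive summaries do not need one. The sponsor should also reconcile Protocol 3.2, whose general order of procedures lists a standing reading pre-dose, post-dose and at outpatient visits, with Tables 5 and 6, which restrict it to specified times. The set of paired times will then be unambiguous.

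The cost is SAP wording, one derived variable and one table for the 37 participants recruited. No new measurement is needed.

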- PQP has a Terminal Elimination Half-life of approximately 22 days. However, approximately 1 % of the Cmax is predicted on 672 hours (i.e. 28 days) after the administration of 1280 mg in healthy adults [22]. Therefore, a follow-up of 30 days (i.e. 28 days after last dose) is considered acceptable to ensure that possible delayed effects on safety laboratory tests are appropriately documented.

Close clinical monitoring will include LFT measurements (including AST, ALT, bilirubin and alkaline phosphatase [ALP]) and ECG measurements in triplicate. Participants will remain in the unit under medical supervision until at least 48 hours following the final dose (i.e. at least 120 hours [h] inpatient) and will be followed up to Day 30 (+/-1 day).

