Haematological system	
PQP: Haematological indices did not change as a result of PQP administration [25].
 
Anaemia and a reduction of haemoglobin commonly seen with DHA-PQP use. [25]
 
PYR: eosinophilia, neutropenia, anaemia, reduced haemoglobin and increased platelet count [19].
	1) Specific inclusion and exclusion criteria will be used to select potential participants. 2) Close monitoring of full blood count (including haemoglobin, white blood cell/neutrophil and platelet count) will be conducted at regular intervals throughout the trial. 3) Specific AR rules related to haematology.

Target System	Effect	Risk Mitigation
Gastrointestinal system	PQP : gastrointestinal disturbances such as nausea/vomiting, abdominal pain and diarrhoea [9,10].	1) Standard monitoring as with all early phase studies. 2) Regular biochemistry blood samples
	PYR : nausea/vomiting (2.2 % to 2.5 %), abdominal pain, diarrhoea and constipation [8].	
Reproductive system	POP : no specific data relating to the effects of PQP on human fertility; however, to date no AEs have been reported during clinical use [25]. Animal studies: In reproductive studies, PQP did not induce malformation in rats or rabbits [25].	1) Specific contraceptive requirements will be in place for participants. 2) Contraceptive guidance will be used in Inclusion Criteria (Section 5.3). 3) Female participants will need evidence of negative pregnancy tests prior to dosing.
	PYR : no adequate data on the use of pyronaridine alone in human pregnancy or lactation. Animal studies: pyronaridine did not show any teratogenic effects nor effects on fertility or reproductive performance were observed at doses three-fold higher than the proposed human exposure [19].	

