**Table 9: Individual rules (decision 1)**

Adverse Events Related to Trial Drug	Actiona
Moderate (Table 14) except QT interval prolongation, haematology, and liver function, for which rules are specified below)	Trial drug administration may be continued, delayed, temporarily suspended or discontinued in accordance with Investigator's clinical judgment
Moderate LFT increases: ALT or AST value $>3 \times$ and $<5 \times$ ULN	
QT interval prolongation: A prolongation of the uncorrected QT interval of greater than 500 ms, using consistent, technically valid triplicate ECG	Trial drug administration will be discontinued.
Haematology: a) Hb drop of $>25\%$ from baseline on Day-1 (only for values below the laboratory reference range), or to an absolute value of $<100\text{ g/L}$ b) Platelet count drop of $> 25\%$ from baseline on Day-1 (only for values outside the laboratory reference range), or absolute value of $<80 \times 10^9/\text{L}$ c) Clinically significant neutrophil drop b	
Severe (Table 14) except liver function, for which rules are specified below.	
ALT or AST value $>3 \times$ and $<5 \times$ ULN, and symptomatic or ALT or AST value $>5 \times$ ULN +/- symptoms b	
Serious (fatal or life-threatening)	
Serious LFT increase: ALT or AST value $>3 \times$ ULN together with bilirubin $>1.5 \times$ ULN, without other evidence of cholestasis	

aActions are only relevant for dosing regimens where additional doses are planned for administration.

bSymptoms include fatigue, nausea, vomiting, right upper quadrant pain or tenderness, fever, rash and/or eosinophilia (eosinophil percent or count above the ULN). Abbreviations: ALT: alanine aminotransferase; AST: aspartate aminotransferase; ECG: Electrocardiogram; Hb: Haemoglobin; ms: milliseconds; QT: QT interval; ULN: upper limit of normal.

\*Investigator judgement will be used to determine which of the pre-dose measurements are considered the baseline. Where possible, the baseline value should be the one that was taken at the closest time of day to the samples being assessed for change, to account for diurnal variation (for example, the D-1 morning blood samples)

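### The individual haematology discontinuation rule in Protocol Table 9 has no scheduled blood count to act on between doses 2 and 3, and possibly none during the whole dosing period

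*Protocol*

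**What the plan says.** **Dosing.** Protocol Table 5, note 10: "Dosing will be carried out in fasted state on the morning of each dosing day (Days 1, 2 and 3". There are three doses, the last on the morning of Day 3.

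**Safety bloods.** The biochemistry, haematology and coagulation row of Table 5 is marked at screening, on Day -1, on Days 1 to 6, on Day 7 (sentinel group only), and on Days 8, 15, 22 and 30. The Day 2 and Day 3 marks carry footnote 12: "On Day 2 and Day 3, only the following safety blood tests will be measured: AST, ALT, bilirubin". Table 6, which gives clock times on dosing days, has no laboratory column. Section 3.2 lists haematology in both the pre-dose and the post-dose order of procedures.

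**Individual rules.** Table 9 (Section 4.4) has a haematology row with haemoglobin, platelet and neutrophil criteria. The action printed beside the QT row, "Trial drug administration will be discontinued", is read here as a merged cell that also covers the haematology, severe, liver and serious rows below it. Footnote a adds: "Actions are only relevant for dosing regimens where additional doses are planned for administration".

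**Mitigation.** For the haematological system, Table 3 lists blood-count monitoring at regular intervals and "Specific AR rules related to haematology".

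**The concern.** A discontinuation rule for an individual protects that person only if a result can arrive while a dose can still be withheld. Here the schedule omits the analytes that the haematology row needs on the two days when withholding a dose is still possible after dosing has begun. A site that follows Table 5 exactly would give the third dose with no scheduled blood count reflecting the second. It might also give the second and third doses with none reflecting the first.

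The protocol relies on this protection. Section 1.1 describes the study as, to the sponsor's knowledge, the first human study of the combination. The Introduction names eosinophilia, neutropenia and anaemia among the more frequently reported events with pyronaridine. An asymptomatic fall in haemoglobin, platelets or neutrophils gives no clinical sign that would prompt an unscheduled test.

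**Working it through.** The plan gives no figure on this point, so the check is a count of scheduled panels against dosing times.

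**Inputs**
- Doses (Table 5, note 10), in nominal hours from the first dose: 0, 24 and 48.
- Full panels that include haematology (Table 5, marks without footnote 12): Day 1 at an unstated time *t*, then Day 4 (about 72 h if taken in the morning), Day 5 and later.
- Day 2 and Day 3 draws (footnote 12): AST, ALT and bilirubin only. Clock time and turnaround of results are not given.

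**Count of scheduled blood counts that fall between doses**

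| Day 1 draw | Dose 1 to dose 2 (0–24 h) | Dose 2 to dose 3 (24–48 h) | Dose 1 to dose 3 |
|---|---|---|---|
| Pre-dose (*t* < 0) | 0 | 0 | 0 + 0 = 0 |
| Post-dose (*t* > 0, on Day 1) | 1 | 0 | 1 + 0 = 1 |

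The first blood count that is certain to follow a dose is on Day 4, about 72 − 48 = 24 h after the last dose. At whatever hour it is drawn, it comes too late for an individual action under footnote a.

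**Rows of Table 9 that lead to discontinuation.** There are six: QT, haematology, severe reaction, symptomatic or severe liver increase, serious reaction, and serious liver increase. Set against footnote 12:
- *Haematology:* none of its three analytes is scheduled on Day 2 or Day 3. This row lacks its trigger data.
- *Symptomatic or severe liver increase:* ALT and AST are measured. The footnote's list of symptoms ends with "rash and/or eosinophilia (eosinophil percent or count above the ULN"), so eosinophilia is one of several alternatives. Only that route lacks scheduled data. The other symptoms still count, and values above 5 × ULN need no symptom.
- *Serious liver increase:* the triggers, ALT or AST with bilirubin, are exactly what is measured. Absence of other evidence of cholestasis is a qualifier. Without ALP and GGT it cannot be fully checked, but the rule can still fire.
- *QT, severe and serious reactions:* these do not rest on the omitted analytes in the same way. ECGs and clinical assessment are scheduled on all dosing days.

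The result is one row of six without scheduled trigger data, one with a single route missing, and one with a qualifier that is only partly checkable.

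**The case against.** A reader might infer that three of the six rows cannot operate, that no haematology rule can act before the last dose, and that the stated individual protection is absent. The documents do not support that, for these reasons:

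- **Liver rows.** Neither eosinophilia nor cholestasis is a stand-alone criterion, and the liver triggers are measured on Days 2 and 3.
- **Day 1 panel.** It may be post-dose. If so, and if the result is back in time, it could inform the second and third doses.
- **Discretion.** Table 7 lets the investigator add assessments for an individual, or add parameters to a sample already scheduled. Section 3.3 allows individual-safety features to be used at the investigator's discretion. Symptom-directed examinations are scheduled daily in-house.
- **Moderate liver row.** A participant with ALT of 3 to 5 × ULN and undetected eosinophilia is not bound to continue. That row leaves the choice, discontinuation included, to the investigator's judgement.
- **Cohort rule.** The haematology rule in Table 10 works on results from Day 4 onward, including sentinel data to Day 15, before the other 30 participants are dosed.
- **Monitoring text.** Table 3 promises regular blood counts, not daily ones. The Introduction includes ALP in close monitoring without naming days.
- **Timing.** The documents give no evidence that haematological effects appear within the 48 h between the first and last dose.

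All of this stands, and it confines the point to the haematology row. It does not remove it. Discretionary tests need a prompt, which an asymptomatic fall does not give. The cohort rule protects those dosed later, not the person already being dosed. Whatever the hour of the Day 1 draw, the count between doses 2 and 3 remains 0.

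**Conclusion.** The point holds for the haematology row. Between doses 2 and 3 the individual haemoglobin, platelet and neutrophil rule has no scheduled data. Over the whole dosing period it has 0 or 1 scheduled post-dose blood counts, depending on a draw time that the protocol does not state. This is one of six discontinuation rows. The gaps in the eosinophilia route and the cholestasis qualifier are lesser points, since both liver rules can still fire.

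The conclusion rests on two things: reading the Table 9 action as a merged cell, and taking footnote 12 as written. The chance that a participant would meet a haematology criterion in this window cannot be estimated from the documents, so the size is given as missing measurements, not as expected events. The mismatch still needs correcting, because the rule is cited as a mitigation and scheduled data cannot trigger it for at least the second dosing interval.

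**What to change.** - Reconcile Table 5 footnote 12, the haematology row of Table 9 and the haematological entry in Table 3. Either the scheduled tests supply the data that the rule uses, or the tables say plainly that the individual haematology rule has no scheduled data on Days 2 and 3. The choice belongs to the sponsor's safety group, and this review does not propose a rule.
- State the Day 1 laboratory draw time relative to dosing.
- In the same edit, note that on Days 2 and 3 eosinophils, ALP and GGT are not scheduled, and how the two liver rows are then to be read.

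**Cost.** This is a footnote and table edit by amendment. Blood is already drawn on Days 2 and 3, so the burden is at most an added tube at existing draws. The total must be checked against the 470 mL cap in Section 7.12, because the documents give no planned volume.

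SAP Section 3.2 says that recruitment stopped at 37. If dosing is already complete, the schedule cannot be changed. The study report should then say that an absence of haematology-triggered discontinuations partly reflects the absence of scheduled blood counts, and is not by itself evidence of tolerability.
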